2. STUDY OBJECTIVES

2.1 Primary Objective(s)

To evaluate the safety, tolerability and efficacy of 2 doses (0.0014% and 0.003%) of topical ophthalmic AR-15512 compared to its vehicle administered BID in subjects with DED.

[figure not shown]
3. INVESTIGATIONAL PLAN

3.1 Overall Study Design and Plan

This will be a Phase 2b, multicenter, vehicle-controlled, double-masked, randomized study conducted at approximately 15 sites in the United States. All subjects enrolled will have DED. The study will consist of Screening and Baseline visits as well as follow-up visits at Day 14 (Visit 3), 28 (Visit 4) and 84 (Visit 5 / Study Exit). All subjects will be exposed to the CAE at the Screening, Baseline, Day 28 and Day 84 visits. A summary of the overall study design is found in Figure 2.

At the end of the Screening Visit, all qualified subjects will be assigned to administer study vehicle BID to both eyes for 14 days (vehicle run-in period). After the vehicle run-in period, subjects will be re-evaluated for signs and symptoms of DED. Only subjects who requalify, based on inclusion/exclusion criteria, will be enrolled in the study and randomized at a 1:1:1 ratio within each site, to receive AR-15512 0.0014%, AR-15512 0.003% or AR-15512 vehicle to be administered as 1 drop in each eye twice daily for 84 days. Efficacy will be assessed on Visit 3 without use of the CAE and at Visits 4 and 5 pre-, during and post- use of the CAE. Safety assessments will be conducted at each study visit. At the end of Study Visit 5, the subject will exit the study. A summary of all study assessments per visit can be found in Appendix 4 (Schedule of Visits and Procedures).

Figure 2 Study Design

3.2 Rationale for Study Design and Control Group

AR-15512 is a TRPM8 receptor agonist that modulates activation of cold thermoreceptor nerve terminals of the cornea leading to potentially a dual role mechanism for the treatment of DED; increased tear production and reduction of ocular discomfort and pain. Both pre-clinical and clinical findings support this hypothesis.

In vivo topical administration of AR-15512 was shown to increase tear production and blink rate in guinea pigs and TRPM8 knockout mice are characterized by dramatically reduced basal tearing and an abrogated cold responsiveness without any effect on nociceptor-mediated irritative tearing (Dhaka 2007).

Data from a recently completed Ph1/2a study in subjects with DED provided initial proof of concept for AR-15512 in the treatment of DED.

The results of the Phase 2b clinical study will be used to optimize future study designs.

3.3 Study Duration and Dates

The approximate duration of subject participation is approximately 14 weeks (14 days vehicle run-in period before randomization followed by 12 weeks of randomized treatment administration).

4. STUDY POPULATION SELECTION

4.1 Study Population

[figure not shown]
This study is anticipated to enroll approximately 360 subjects with DED as defined below in Sections 4.2 and 4.3 so as approximately 324 subjects complete Day 84. The anticipated dropout rate is 10%. To achieve this goal, approximately 1500 subjects may be screened.

4.2 Inclusion Criteria

Subjects must meet all of the following criteria to enter into the study:

- 1. Male or female, 30 years of age or older at the Screening visit
- 2. Have a previous history of DED, clinician diagnosed or patient reported, within the previous 6 months
- Have used, and/or desired to use artificial tears for DED symptoms within 2 months prior to the Screening visit

Aerie Pharmaceuticals, Inc.

- 7. BCVA 20/200 (+0.70 LogMAR) or better in both eyes at both the Screening and Baseline visits
- 8. Good general and ocular health, as determined by the investigator using medical history, ophthalmic examination and history, blood chemistry and hematology, urinalysis and vital signs (heart rate and blood pressure) at the Screening visit
- 9. Capable of giving signed informed consent, which includes compliance with the requirements and restrictions listed in the informed consent form (ICF) and in this protocol
- 10. Written informed consent from the subject has been obtained prior to any study related procedures
- 11. Able, as assessed by the investigator, and willing to follow study instructions and likely to complete all required study visits

4.3 Exclusion Criteria

Subjects meeting any of the following criteria during Screening and/or Baseline visits (i.e., qualification visits) as specified below will be excluded from entry into the study:

1. History or presence of any ocular disorder or condition (other than DED) in either eye that would, in the opinion of the investigator, likely interfere with the interpretation of the study results or subject safety, such as: significant corneal or conjunctival scarring; pterygium or nodular pinguecula; conjunctivitis, or inflammation not associated with DED; anterior (epithelial) basement membrane

- corneal dystrophy or other clinically significant corneal dystrophy or degeneration; evidence of keratoconus; etc. (Note: Blepharitis and/or Meibomian gland disease not requiring treatment are allowed.)
- 2. Current evidence of other significant ophthalmic disease requiring topical medication (e.g. glaucoma, ocular hypertension), which may interfere with vision (e.g., cataract, macular degeneration) or other disease which the investigator believes may interfere with study findings or interpretation
- 3. History of ocular surgery within 1 year prior to the Screening visit, including punctal cautery, corneal refractive, or anterior segment surgeries that affect corneal sensitivity (e.g., cataract surgery or any surgery involving limbal or corneal incision)
- 4. Have had a corneal transplant in either or both eyes
- 5. Use of contact lenses in either eye within 7 days prior to the Screening visit or planned use during the study
- 6. Punctal or intracanalicular plug present in either eyelid within 1 year prior to the Screening visit or anticipated plug insertion or occlusion at any time during the study
- 7. Use of artificial tears within 2 hours prior to the Screening visit or anticipated use during the study
- 8. Regular use of lid hygiene within 14 days prior to the Screening visit or any planned use during the study
- 9. Regular use of any topical ocular medications (including use of ocular cyclosporine or other prescription ophthalmic solution for DED (e.g., Restasis®, CequaTM, Xiidra®), topical ocular corticosteroid- or non-steroidal-anti-inflammatory agents, glaucoma medications, eye whitening products (e.g., Visine®, Lumify®), topical antibiotics, topical antihistamines, mast cell stabilizers or other over-the-counter [OTC], herbal, prescription, or nutritional supplements with the exception of artificial tears), within 30 days prior to the Screening visit or anticipated use during the study. Note: Occasional (as needed) > 24 hours prior to the Screening Visit may be permitted
- 10. Use of medications associated with the treatment of severe DED and/or Meibomian gland disease such as oral pilocarpine, oral cevimeline, oral macrolides, oral tetracyclines, oral tetracycline derivatives, and oral retinoids within 90 days prior to the Baseline Visit or anticipated use during the study
- 11. Use of systemic corticosteroids started < 90 days prior to the Baseline Visit or a change in dosage is anticipated during the study. Note: Non-ocular topically applied corticosteroids (including nasal sprays and inhalers) will be permitted during the study and the dose is not required to be stable
- 12. Use of TrueTear® within 45 days of the Screening visit or anticipated use during the study
- 13. Use of lid heating therapy (i.e., LipiFlow®, iLUX®) or Meibomian gland probing/therapeutic expression within 1 year prior to the Screening visit or anticipated during the study

- 14. Use of systemic immunomodulators (e.g., hydroxychloroquine, methotrexate, cyclosporine) started < 90 days prior to the Baseline Visit or a change in dosage is anticipated during the study
- 15. Any systemic medication known to cause ocular drying (e.g. antihistamines, antidepressants, beta-blockers) started < 14 days prior to the Screening visit or a change in dosage is anticipated during the study. Note: Occasional (as needed) use of medications such as systemic antihistamines will be permitted
- 16. Diagnosis of recurrent, ongoing, or active ocular infection including, but not limited to herpes simplex or zoster, vaccinia, varicella, tuberculosis of the eye, acanthamoeba, or fungal disease
- 17. At the Screening visit, at the investigator's discretion, have active or uncontrolled, severe:
 - a. Systemic allergy
 - b. Chronic seasonal allergies at risk of being active during the study
 - c. Rhinitis or sinusitis
- 18. History or presence of significant systemic disease (i.e.: cardiovascular, pulmonary, hepatic, renal, hematologic, immunologic). Significant is defined as any disease that, in the assessment of the Investigator, would put the safety of the subject at risk through participation, or which would prevent or confound protocol-specified assessments (e.g., severe Sjögren's syndrome, severe rheumatoid arthritis, severe systemic lupus erythematosus, uncontrolled immunodeficiency disease, etc.)
- 19. Current enrollment in an investigational drug or device study or participation in such a study within 30 days prior to the Baseline Visit
- 20. Known allergies or sensitivity to the study interventions or study diagnostic agents including sodium fluorescein, lissamine green, etc.
- 21. Positive pregnancy test at Screening or Baseline visits or currently breastfeeding or plans to become pregnant or breastfeed during the study
- 22. Women of childbearing potential who are not using a medically acceptable form of birth control
- 23. The subject has a condition or is in a situation that, in the Investigator's opinion, may put the subject at significant risk, may confound the study results, or may interfere significantly with the subject's participation in the study
- 24. Employees directly involved in the AR-15512-CS201 trial at the clinical site.

4.4 Study Eye Criteria

The study subject must have one eye (the same eye) meeting all the inclusion criteria (Section 4.2) and none of the exclusion criteria (Section 4.3). Study subjects will be dosed in both eyes. If both eyes are eligible at the time of randomization, the study eye will be defined as the eye with the higher pre-CAE Ora Calibra ODS score at the Baseline visit. If both eyes qualify and have the same pre-CAE Ora Calibra ODS score, then study eye will be defined as

the eye with the lowest anesthetized Schirmer score at the Baseline visit. If both eyes still qualify, the right eye will be designated as the study eye.

5. STUDY TREATMENTS

5.1 Description of Treatments

5.1.1 Study Drug

AR-15512 ophthalmic solution is a sterile, preservative-free, isotonic, buffered aqueous solution containing AR-15512 (0.0014% or 0.003%), hypromellose, polyoxyl 35 castor oil, sodium dihydrogen phosphate dihydrate, and sodium chloride in water (either purified water or water for injection). The product formulations are adjusted to a pH of approximately 7 with sodium hydroxide and are packaged in blow-fill-seal containers of extruded polyethylene.

Study drug will be provided in masked identical kits:

- AR-15512 ophthalmic solution, 0.0014%
- AR-15512 ophthalmic solution, 0.003%

5.1.2 Vehicle (Placebo) or Control Drug

AR-15512 ophthalmic solution vehicle is a sterile, preservative-free, isotonic, buffered aqueous solution containing hypromellose, polyoxyl 35 castor oil, sodium dihydrogen phosphate dihydrate, sodium chloride in water (either purified water or water for injection). The product formulation is adjusted to a pH of approximately 7 with sodium hydroxide and is packaged in blow-fill-seal containers of extruded polyethylene.

AR-15512 vehicle will be provided in masked identical kits identical to the study drug.

5.2 Treatments Administered

AR-15512 (0.0014% and 0.003%) as well as AR-15512 vehicle will be provided as single use blow-fill-seal containers of extruded polyethylene.

5.3 Selection and Timing of Dose for Each Patient

Subjects who qualify at the Screening visit will be instructed on proper administration procedure to administer 1 drop of AR-15512 vehicle BID to both eyes on Days -14 to -1 (vehicle run-in period).

Following the vehicle run-in period, those subjects who requalify at the Baseline visit, will be randomized into 3 groups, in a 1:1:1 ratio within each site, as follows:

- AR-15512 0.0014% (N = 120)
- AR-15512 0.003% (N = 120)
- AR-15512 vehicle (N = 120)

Subjects will be re-instructed on proper administration procedures at the Baseline visit. Subjects will be instructed to administer their randomized study treatment BID to both eyes as follows: 1 drop in each eye in the morning (from approximately 7:00h to 10:00h) and 1 drop in each eye in the evening (from approximately 19:00h to 22:00h).

5.4 Method of Assigning Patients to Treatment Groups

All subjects will be centrally assigned to randomized study treatment using an interactive web response system (IWRS). Before the study is initiated, the log-in information and directions for the IWRS will be provided to qualified personnel at each site.

All qualified subjects will be assigned to receive AR-15512 vehicle BID to both eyes for 14 days (vehicle run-in period). Following the run-in period, all subjects who requalify at the Baseline visit (Day 1 [Visit 2]), will be randomized in a 1:1:1 ratio, within each site, to receive AR-15512 0.0014%: AR-15512 0.003%: AR-15512 vehicle. The IWRS will provide the site with the specific kit number(s) for each randomized subject at the time of randomization. Sites will dispense the study treatment according to the IWRS instructions and the Schedule of Visits and Assessments (Appendix 3).

5.5 Masking

During the vehicle run-in period, the subject will be masked. During the randomized treatment period, the investigator and site staff performing eligibility / efficacy and safety assessments and the subjects will be masked. Subjects will be informed that they all will receive vehicle at some point in the study, but the exact timing will not be specified.

AR-15512 (0.0014%), AR-15512 (0.003%) and AR-15512 vehicle will be provided in identical single-use blow-fill-seal containers.

The staff members who administer the treatment drop at each visit will not be allowed to participate in any efficacy or safety-related assessments post-drop administration.

5.6 Unmasking

A randomization schedule for allocating the treatments within a site will be prepared by an unmasked statistician who is not involved in the day-to-day conduct of the study.

Treatment assignments will be masked to the Investigator, the clinical study team (Sponsor, personnel involved in day to day study management, Monitors, Data Managers, and Statisticians), and the subjects. Only in case of medical emergency or occurrence of adverse events that warrant unmasking in the opinion of the investigator, will the treatment assignment(s) be unmasked and made available to the Investigator and the Medical Monitor. In the absence of medical need, the randomization code will not be available to the above personnel until after the study is completed and the database is locked.

If the Investigator feels it is necessary to unmask a subject's treatment assignment after an emergency situation, the Investigator should contact the Medical Monitor or designee. Only after consultation with the Medical Monitor will a decision be made as to whether or not the treatment for the subject should be unmasked. The treatment assignment will be revealed on a subject-by-subject basis, thus leaving the masking on the remaining subjects intact.

5.7 Concomitant Therapy

Any therapy or intervention (including OTC, prescription medicines, vitamins and herbal supplements) that the subject is receiving at the time of screening or receives during the study must be recorded along with:

- Indication
- Dates of administration including start and end dates
- Dosage information including dose and frequency

From the Screening visit to the end of the study (Visit 5 or early termination), site staff will question each subject specifically on the use of concomitant therapies and interventions. Site staff must notify Aerie immediately if a subject consumes or applies any concomitant treatments or interventions that are not permitted by the protocol.

Use of the following as concomitant therapy or interventions during the study is prohibited:

• Regular use of any topical ocular medications (including use of ocular cyclosporine or other prescription ophthalmic solution for DED (e.g., Restasis[®], CequaTM, Xiidra[®]), topical ocular corticosteroid- or non-steroidal-anti-inflammatory agents, glaucoma medications, eye whitening products (e.g., Visine[®], Lumify[®]), topical

- antibiotics, topical anti-histamines, mast cell stabilizers or other OTC, herbal, prescription, nutritional supplements or artificial tears)
- Systemic immunomodulators (e.g., hydroxychloroquine, methotrexate, cyclosporine) started < 90 days prior to the Baseline Visit or a change in dosage is anticipated during the study
- Cyclosporine administered through any route
- Systemic corticosteroids administered through any route (e.g. oral or IV) started < 90 days prior to the Baseline Visit or a change in dosage is anticipated during the study
- Medications associated with the treatment of severe DED and/or Meibomian gland disease (e.g., oral pilocarpine, oral cevimeline, oral macrolides, oral tetracyclines, oral tetracycline derivatives, and oral retinoids)
- Contact lens wear in either eye
- Punctal or intracanalicular plugs
- Lid-heating therapy (ie, LipiFlow, iLUX, etc.), Meibomian gland probing, or therapeutic Meibomian gland expression
- Regular use of lid hygiene
- Any systemic medication known to cause ocular drying (e.g. antihistamines, antidepressants, beta-blockers) started < 14 days prior to the Screening visit or a change in dosage is anticipated during the study. Occasional (as needed) use of medications such as systemic antihistamines will be permitted

Occasional (as needed) use of medications such as non-prescription anti-inflammatories / pain relievers (e.g. aspirin, acetaminophen etc.), and acid-reflux/heartburn medications will be permitted. Occasional (as needed) use of cold/flu medications that **do not** contain antihistamines will be permitted. Cold/flu medications that **do** contain antihistamines are discouraged but will be permitted (please refer to the Allowed Concomitant Medication List). In addition, all systemic medications (including OTC and herbal), not listed in Exclusions are allowable. Skin care products containing retinoids are allowable.

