- a. The use of these therapies is allowed during the study provided that the dosing regimen is stable for at least 14 days prior to the Screening visit and does not change at any time during the study duration. The total time for washout if one of the systemic medications known to cause ocular dryness was stopped is 14 days relative to Screening visit.
- b. The use of these therapies is allowed during the study provided that the dosing regimen is stable for at least 90 days prior to the Baseline Visit and does not change at any time during the study duration. The total time for washout if one of these medications was stopped is 90 days relative to Baseline Visit

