5.9 Permitted Interventions

Therapy considered necessary for the subject's welfare may be given at the discretion of the investigator. If the use of a specific therapy or intervention is in question, please contact Aerie.

Use of the following is permitted during the study:

- Any systemic medication not itemized as an exclusion in Section 4.3 is permitted.
- Occasional (as needed) use of medications such as non-prescription antiinflammatories / pain relievers (e.g. aspirin, acetaminophen etc.), and acidreflux/heartburn medications will be permitted.
- Occasional (as needed) use of and cold/flu medications that **do not** contain antihistamines will be permitted. Cold/flu medications that **do** contain antihistamines are discouraged but will be permitted (please refer to the Allowed Concomitant Medication List).
- Skin care products containing retinoids are permitted.

Any medication taken during the study between the date of the first dose of randomized study treatment and the date of the Exit visit or Early Termination visit should be recorded in the case report form (CRF) as a concomitant medication.

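### Protocol 5.7 contradicts itself and the eligibility rules on stable systemic cyclosporine, and does not match them on artificial tears

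*Protocol*

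**What the plan says.** **Cyclosporine.** Exclusion 14 (Protocol 4.3) rules out "Use of systemic immunomodulators (e.g., hydroxychloroquine, methotrexate, cyclosporine) started < 90 days prior to the Baseline Visit", or an expected change of dose. Footnote b to Table 1 (Protocol 5.8.1) covers the same drug class and says: "The use of these therapies is allowed during the study provided that the dosing regimen is stable for at least 90 days" before Baseline and does not change afterwards. Protocol 5.7 repeats the conditional rule as a prohibition on "Systemic immunomodulators (e.g., hydroxychloroquine, methotrexate, cyclosporine) started < 90 days prior to the Baseline Visit", again with the dose-change alternative. Its next bullet prohibits "Cyclosporine administered through any route", with no exception for a stable dose. Protocol 5.9 adds: "Any systemic medication not itemized as an exclusion in Section 4.3 is permitted".

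**Artificial tears.** Exclusion 7 rules out "Use of artificial tears within 2 hours prior to the Screening visit or anticipated use during the study". Exclusion 9, on regular use of topical ocular medications, exempts tears. The matching bullet of 5.7 includes them: its list ends with "mast cell stabilizers or other OTC, herbal, prescription, nutritional supplements or artificial tears", and the whole list is governed by an opening limit to regular use. Protocol 5.7 has no separate bullet for tears. Table 1 gives tears their own row, with a 2-hour washout before Screening.

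**What hangs on it.** Protocol 5.7 requires sites to tell the sponsor at once about any treatment that is not permitted. Protocol 10.10 names concomitant medication restrictions among typical significant deviations. Protocol 9.4.2 and SAP 4.2 remove subjects with significant deviations from the per-protocol population.

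**The concern.** A site, a monitor and the deviation reviewers all need one answer to whether a therapy is prohibited. For stable systemic cyclosporine the protocol gives two. The same subject is properly enrolled under one section and in breach under another, and notification, deviation status and per-protocol membership follow whichever is applied.

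For tears the open question is use that was not anticipated at entry and is not regular. It is a realistic case: an inclusion criterion selects people who used or wanted tears in the two months before Screening, and Protocol 1.2.3 describes tears as soothing and lubricating the eye surface. The pre-CAE ODS-VAS asks about discomfort over the last 24 hours (Protocol 6.6.1), so a drop used on the day before Visit 4 lies inside the period being rated. Change in this score at Day 28 for the 0.003% arm is also the first test in the fixed sequence (Protocol 9.2).

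**Working it through.** **Step 1. Cyclosporine: apply each rule to one subject.** Take a subject on systemic cyclosporine whose dose has been stable for at least 90 days before Baseline, with no change expected.

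| Place | Result for this subject |
|---|---|
| Exclusion 14 | Not excluded |
| Table 1, footnote b | Expressly allowed during the study |
| 5.7, immunomodulator bullet | Not prohibited |
| 5.9 | Points to permitted, since 4.3 does not exclude a stable regimen |
| 5.7, next bullet | Prohibited |

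Two ways of removing the conflict fail. Reading the last bullet as ocular only does not fit its reference to any route, and ocular cyclosporine is already named in the topical bullet of 5.7. Reading it as an override leaves the naming of cyclosporine in the immunomodulator bullet without effect, and still contradicts footnote b.

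**Step 2. Tears: apply each rule to one subject.** Take a subject who expected to use no tears, was enrolled, and then uses a drop once or twice before Visit 4.

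| Place | Result for this subject |
|---|---|
| Exclusion 7 | Not met at entry, because no use was anticipated |
| Exclusion 9 | Does not apply; tears are exempt |
| Table 1 | Sets a washout before Screening only |
| 5.7, topical bullet | Bars regular use; occasional use not clearly covered |

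The distinction between regular and occasional use is the protocol's own. Exclusion 9 and Table 1 both note that as-needed use of topical medications more than 24 hours before Screening may be permitted. The direction differs from cyclosporine: for tears the entry rule is the stricter one. Exempting tears from Exclusion 9 does not make a planned tear user eligible, because Exclusion 7 still applies.

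**Step 3. Does any stated figure depend on this?** Inputs from Protocol 9.3: 108 per group, two-sided alpha 0.05; ODS-VAS difference 8.5 with SD 19.0; Schirmer difference 1.4 mm with SD 3.15 mm. Power ≈ Φ(δ / (SD × √(2/n)) − 1.96).

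- ODS-VAS: 19.0 × √(2/108) = 2.586; 8.5 / 2.586 = 3.288; Φ(1.328) = 90.8% (90.5% by noncentral t).
- Schirmer: 3.15 × √(2/108) = 0.4287; 1.4 / 0.4287 = 3.266; Φ(1.306) = 90.4% (90.2% by noncentral t).
- Randomized per arm: 108 / 0.90 = 120.

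All three reproduce the plan. None takes concomitant therapy as an input, and the primary analysis uses all randomized subjects as randomized (Protocol 9.4.1, SAP 4.1). Reconciling the wording changes none of them.

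**The case against.** The best reply is that the protocol already contains most of what is needed. Exclusion 7 carries no limit to regular use. Table 1, which by its title concerns prohibited therapies, gives tears a row of their own. The occasional uses expressly permitted in 5.7 and 5.9 do not include tears. Protocol 5.9 sends doubtful cases to the sponsor, and an allowed-medication list is cited that is not among the documents. The sponsor designates deviations centrally before database lock (Protocol 10.10), and major violations are judged masked (SAP 5.2). All of this stands, and it is why the tear point is that occasional use is not *clearly* prohibited, rather than that it is allowed. It does not settle cyclosporine, where central review would still have to choose between two opposite rules.

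Three stronger readings are tempting and not supported.

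- *Both therapies make an eligible subject a deviator.* This is true of cyclosporine only. For tears the mismatch runs the other way.
- *Tear use would go unnoticed.* Protocol 5.7 requires every therapy, including over-the-counter products, to be recorded with indication, dates, dose and frequency, and requires staff to question each subject specifically. The gap is in classification.
- *Tear use weakens both primary endpoints and costs power.* The documents give no rate of use, no difference between arms and no size of effect, and any effect on the anesthetized Schirmer score is inference. The answer is set by the assumptions. A 5-point ODS-VAS effect with a 5-percentage-point excess on vehicle shifts the difference by 5 × 0.05 = 0.25, to 8.25, and power is about 89%. A 10-point effect with a 20-point excess shifts it by 2.0, to 6.5, and power is about 71%. Neither case can be chosen from the documents. Since the primary analysis is intent-to-treat, reclassifying deviators would not recover any such loss.

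**Conclusion.** The point holds: Protocol 5.7 is wrong as written, as an internal contradiction of low to moderate impact. On cyclosporine the conflict is direct, both with Exclusion 14 and footnote b and between adjacent bullets of 5.7. Its reach is deviation status, sponsor notification and per-protocol membership, probably for few subjects; that is a judgement, since the documents give no count. On tears the entry rule and the on-study rule do not match, which leaves unplanned occasional use after entry unclear. A bearing on the ODS-VAS primary is plausible because of its 24-hour recall, but cannot be sized. The primary analysis and the 90% power statements are unaffected. Parts of both documents are blacked out, and handling of prohibited therapy may be set out there, so its absence is not claimed.

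**What to change.** Reconcile Protocol 4.3 (Exclusions 7, 9 and 14), 5.7, 5.9 and Table 1 with footnote b, so that stable systemic cyclosporine has one rule and artificial tears have one rule wherever they appear. Which rule to adopt is a clinical decision for the sponsor. Apply the reconciled rule to every subject at the masked deviation review before database lock, using the concomitant-therapy records that 5.7 already requires.

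The cost is a protocol clarification and a note to sites. The sample size, the primary analysis and data collection do not change.
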